Patients who were given intravenous crystalloid boluses before the induction of general anaesthesia did not significantly impact haemodynamic instability [7].

Yet, there are very limited studies and no clear evidence regarding whether preoperative fluid infusion therapy can improve the postoperative prognosis of patients undergoing general anaesthesia. Considering the benefits achieved through preoperative infusion in relation to post-induction hypotension, we thus hypothesize that preoperative fluid infusion can have an impact on

postoperative complications. Additionally, whether the reduction in post-induction hypotension acts as a mediating effect will also be explored.

COIN (Colloid infusion for Optimal outcomes In Non-cardiac surgery(COIN): a randomized controlled trial. Rationale and Design) aims to investigate whether the preoperative colloid infusion before the induction of anesthesia can reduce the postoperative complications of patients planning to undergo non-cardiac surgery with general anaesthesia comparing to crystalloid. The study is a parallel group, blinded, prospective, randomised controlled, multicentre trial with 1 : 1 allocation ratio.

The trial commenced in July 12, 2023 and the estimated timeline for completion of patient accrual was Mar 31, 2025. The participants will be followed until 30 days after surgery. This statistical analysis plan details the pre-planned analyses and statistical considerations for COIN for transparency of data management and analyses procedures. The trial protocol has been submitted to *BMJ Open* (bmjopen-2025-100293).

STUDY OVERVIEW

Ethics and Study Design

The planned study is a parallel group, blinded, randomised, controlled, multi-centre trial conducted at seven tertiary teaching hospitals across China. The study protocol was initially approved by the institutional review board (IRB)

of the coordinating site (Xijing Hospital: KY20232058-F1) followed by institutional IRB approvals from all participating centres. The informed consent will be obtained from patients before enrollment. One interim analysis was planned at 50% information rate (50% enrolled participants) with primary endpoints at 30 days after surgery) with futility stopping rule.

Study Population

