In order to detect a 13% absolute reduction (from 33% to 26%) for the primary outcome of postoperative complications of Clavien-Dindo Grade \geq I up to 30 days after surgery (a risk ratio of 0.8), with 90% power and an overall type I error rate of 5%, a total of 2020 patients (1010 per arm) are required, accounting for 10% drop-out rate.

Randomisation procedure

Randomisation will occur after obtaining informed consent from the eligible patients and shortly before the index surgical procedure is due to start (last-minute randomization). Patients will be centrally allocated to treatment arms in a 1:1 ratio by permuted block randomization stratified with participant centers. To enter a patient into the COIN trial, research staff at each participant site will log on to a secure web-based randomization platform of Redcap data

entry system and obtain a unique patient identification number and allocation assignment. This information will be only revealed to the unblinded investigator who prepare the intervention fluids.

Datasets for Analyses

All statistical analyses within this study will be performed following the intention-to-treat principle. This implies that patients will be analysed in accordance with the treatment groups to which they were initially assigned, as depicted in Figure 1. It is expected that there will be either no or very minimal losses to follow-up for primary and secondary outcomes considering the prospective feature. Patients with missing primary outcome data will be excluded from the analysis (complete-case analysis approach). Missing data for baseline covariates to be included in the analysis model will be accounted for using multiple imputation.

Participation of individual patient in the study will be terminated if they (or their trusted person) withdraw consent. However, if the investigator discontinues the patient's participation, either temporarily or permanently, for reasons in the patient's best interest, especially when serious adverse events are suspected to be related to the intervention, the patient will remain in the analysis to uphold the intention-to-treat principle. Their data will continue to be collected until 30 days after surgery, which marks the final follow-up.

Modified Intent-to-Treat (m-ITT) population excludes individuals who had their

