To account for potential confounders, the adjusted analysis of primary endpoint will use a logistic regression model, where the primary endpoint as the dependent variable and independent variables to include study group (colloid fluid bolus group vs crystalloid fluid bolus group), adjusting for the relevant confounders (planned surgical procedure complexity grade, ASA grade, gender, age, baseline hemoglobin, and baseline creatinine, NPO duration, fluid administration within 12 hours prior to surgery). Odds ratios (95% confidence intervals) will be reported; for those ORs may potentially be biased approximation for RRs, estimates will be obtained via either binomial regressions or converted using bootstrap methods. We will also develop a logistic regression model accounting for the above variables plus any baseline characteristics that appear on visual review to be potentially imbalanced between the study groups.

To account for the center effects, we will fit a mix-effect model with the primary outcome as dependent variable, including group assignment as a fixed effect and participant center (stratification variable) as a random effect. Potential confounders that included in the model are the same as the logistic regression model. Alternative method to use if mixed-effect models fail to reach convergence:

- Include participant sites as a fixed-effect instead of random effect.
- Remove the fixed effect for participant sites
- Adjust for age, hemoglobin, creatinine, fasting duration, etc as a single

continuous variable.

- Remove the covariates in prespecified order to see if convergence reached: gender, hemoglobin, creatinine, age, surgical complexity, ASA grade.

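### If the centre-effects model fails to converge, the fallback list drops centre, the randomisation stratum, before any covariate

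*SAP*

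**What the plan says.** Under Randomisation procedure, the SAP allocates patients "in a 1:1 ratio by permuted block randomization stratified with participant centers". The trial is a "multi-centre trial conducted at seven tertiary teaching hospitals across China" (Ethics and Study Design).

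Under Secondary Analyses of the primary endpoint, two adjusted models follow one another. The first is a logistic regression on study group and eight covariates: surgical complexity, ASA grade, gender, age, haemoglobin, creatinine, NPO duration and fluid given in the 12 hours before surgery. It has no centre term. The second is introduced with its purpose: "To account for the center effects, we will fit a mix-effect model". It takes "participant center (stratification variable) as a random effect" and uses the same covariates as the logistic model.

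Four unnumbered alternatives are given in case the mixed model does not converge:

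- make site a fixed effect;
- "Remove the fixed effect for participant sites";
- enter age, haemoglobin, creatinine, fasting duration and similar variables in a simpler continuous form;
- remove covariates in a set order, namely "gender, hemoglobin, creatinine, age, surgical complexity, ASA grade".

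**The concern.** The second model has one job that the first does not have, which is to reflect centre. A fallback for it should keep centre and give way on the covariates. This list does the reverse: centre goes at the second step, and no later step brings it back or offers centre with fewer covariates. If the failure comes from a sparse covariate level, removing centre does not treat the cause.

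This is also the only overall treatment estimate for the primary endpoint that carries centre. The chi-squared test and the logistic model do not, and centre otherwise appears only as an effect modifier under Subgroup analyses. The Scope section commits the manuscript to following the plan strictly, so the order of the list matters.

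**Working it through.** **1. The list, read top-down**

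| Step | Change | Centre in model? | Covariates |
|---|---|---|---|
| Start | mixed model | random | all eight |
| 1 | site made fixed | fixed | all eight |
| 2 | site removed | no | all eight |
| 3 | continuous covariates simplified | no | eight, simplified |
| 4 | covariates dropped in order | no | fewer |

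At step 2 the model is study group plus the same eight covariates with no centre term. That is the logistic model of the preceding paragraph.

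**2. The drop order.** The model has eight covariates and the drop order names six. The two left out are NPO duration and fluid within 12 hours. Fasting duration does appear at step 3, so NPO duration can be simplified but not dropped.

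**3. Expected events.** The planned size is 1010 per arm for 33% against 26%, 90% power, 5% type I error and 10% drop-out. The usual two-sided formula gives 890 per arm, and 890 / 0.90 = 989. With continuity correction it gives 919, and 919 / 0.90 = 1022 (or 919 × 1.10 = 1011). The plan's figure therefore reproduces to within about 2%.

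Evaluable patients: 1010 × 0.90 = 909 per arm, 1818 in all. Expected events: 909 × 0.33 + 909 × 0.26 = 300 + 236 = 536.

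**4. What dropping centre does, if it happens.** The conditional log odds ratio was set at ln(0.26/0.74) − ln(0.33/0.67) = −1.046 + 0.708 = −0.338 (OR 0.71). The control rate averaged over centres was 33%, with 909 patients per arm in seven centres. The SAP gives neither centre sizes nor between-centre variation, so both are assumptions: shares of 40, 20, 10, 10, 8, 7 and 5%, and normal centre effects on the logit scale. There were 800 simulated trials per setting. Both models were fitted to the same data, without other covariates.

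| Centre SD | Power, centre fixed | Power, centre dropped | Mean log OR, fixed | Mean log OR, dropped | Shift toward zero | Type I error, fixed / dropped |
|---|---|---|---|---|---|---|
| 0 | 90.8% | 90.6% | −0.341 | −0.340 | under 1% | 4.8% / 4.8% |
| 0.3 | 90.4% | 89.9% | −0.339 | −0.334 | 2% | 5.8% / 5.6% |
| 0.6 | 87.3% | 84.9% | −0.336 | −0.318 | 5% | 5.3% / 5.1% |
| 1.0 | 84.1% | 80.1% | −0.335 | −0.292 | 13% | 4.8% / 3.8% |

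Monte Carlo error is about 0.8 points for type I error and 1.0 to 1.4 points for each power figure.

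A second set of assumed centre sizes (600, 400, 300, 200, 160, 100 and 58; 2500 trials each) gave power with centre fixed and dropped of 90.6% and 89.5% at SD 0.5, 88.0% and 85.7% at SD 0.8, and 86.4% and 83.1% at SD 1.0. The losses of 1.1, 2.3 and 3.3 points are of the same order.

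**5. How often step 2 would be reached.** It needs two failures: the random-centre model, then the fixed-centre model. In the first simulation the fixed-centre model never failed at SD 0.6 or below. At SD 1.0 it failed in 4 of 800 trials under the null and 3 of 800 under the alternative. These fits had no other covariates, so failures caused by sparse covariate levels are not counted.

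**The case against.** **The sequence is inferred.** The bullets are unnumbered, and only the last one claims an order. This is fair, but the second bullet makes sense only after the first, so top-down is the natural reading. If no sequence was meant, the analyst may choose to drop centre at will, and the rule is still not fixed.

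**The step will hardly ever be used, and the analysis is exploratory.** Both parts stand. Under Corrections for Multiple Testing, everything beyond the single primary analysis is treated as hypothesis-generating, and the primary chi-squared test has no centre term to lose.

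A reader might also infer stronger points that the documents do not support:

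- *A small centre with no events would trigger the step.* At the average event rate of (33% + 26%) / 2 = 29.5%, the chance of no events is 0.705^10 = 3% in a centre of 10 patients and 0.705^5 = 17% in a centre of 5. The SAP gives no centre sizes, and the mean is 2020 / 7 ≈ 289. Such a centre need not stop either model: a random intercept is shrunk, and in a fixed-effect fit only that centre's own coefficient diverges. In test fits with an empty centre of 10 patients, whether non-convergence was reported depended on the fitting algorithm. The treatment estimate was unharmed with centre kept in.
- *The smaller odds ratio is bias.* Allocation is balanced within centre. The shift reflects non-collapsibility of the odds ratio, not confounding, and type I error is not inflated.
- *A result without centre would be reported as centre-adjusted.* The SAP does not say so. The nearer consequence is that it duplicates the preceding model.
- *The two covariates missing from the drop order would cause failure.* They would simply be retained, and a model with study group and those two has no evident convergence problem.

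**Conclusion.** The ordering is a real but minor fault. Whenever the second fallback is used, the analysis stops doing what it was introduced to do and repeats one already planned. The trial's main conclusion is not at risk.

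The size rests on assumed centre shares and between-centre SDs of 0.3 to 1.0. In that range the log odds ratio moves 2% to 13% closer to zero, and this secondary analysis loses about 0.5 to 4 points of power. The 0.5-point figure is 4 of 800 trials and should be read as close to nothing. That the step is unlikely rests on seven centres, about 536 events and the low failure rate in fits without covariates.

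**What to change.** State that the alternatives are applied in sequence, and order them as follows:

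1. centre as a random effect;
2. centre as a fixed effect;
3. continuous covariates simplified, with centre kept;
4. covariates dropped in the prespecified order, with centre kept, and with NPO duration and fluid within 12 hours added to that order.

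Delete the site-removal bullet, or move it to the end and require its result to be labelled as not centre-adjusted. A centre-stratified Mantel-Haenszel estimate could serve as the final fallback. It tolerates a centre with no events, but it is optional.

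The cost is an edit to one list in the SAP. No data, patients or change to the primary analysis are involved.

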surgical procedures canceled after randomization, patients who withdrew their consent. The as-treated population is defined by the treatment that was actually received during the trial. This takes into account any deviations from the initially assigned treatment regimen, such as crossovers to the other treatments. The Per-Protocol (PP) population consists of all patients who received the assigned treatment without significant deviations from the protocol. Specifically, the analysis will be restricted to those who completed the full-term intervention as it was initially assigned. Participants with treatment interruptions will be excluded from the PP analysis. The exclusion list will be verified by the steering committee prior to lock of the database. Analyses conducted on these dataset will be treated as supplementary analyses.

General analysis Principles

The COIN trial is designed to assess the impact of preoperative colloid infusion on the occurrence of postoperative complications in surgical patients undergoing non-cardiac surgery with general anesthesia. The estimand is the difference in the incidence of postoperative complications as defined by higher than grade I Clavien-Dindo classification at 30 days after surgery between Colloid bolus administration versus crystalloid bolus administration, in patients undergo elective non-cardiac surgery under general anesthesia. The target population is patients experienced surgery procedure. The patients have the planned surgery canceled after randomization will be excluded from the

primary analyses.

In general, categorical variables are to be compared using χ^2 test or Fisher's exact test. Continuous variables will be compared via t-test or Wilcoxon's rank-sum test. Variable normality will be assessed either via the Shapiro-Wilk test or QQ-plots and residual plots. Variable transformation such as natural logarithm or square root will be applied where necessary, or non-parametric methods (such as Wilcoxon rank sum test) shall be applied.

For the analyses of primary, secondary outcomes, and the process measures, the following information will be presented:

- 📅 The number of patients included in each analysis, by treatment arm
- 📅 A summary statistic of the outcome (such as, number (%), mean (sd), media (IQR), etc), by treatment arm
- 📅 The estimated treatment effect
- 📅 A 95% confidence interval for the estimated treatment effect
- 📅 A two-sided P value

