For all analyses, a significance level of 5% will be used. Multiple comparisons will be conducted without Type I error correction and will be interpreted as exploratory.

Data Presentation and Baseline characteristics

Baseline characteristics will be summarized using descriptive statistics for whole patients cohort and for each treatment group by mean and standard

deviation or median and interquartile range for continuous variables, and the number, frequencies, and percent for categorical variables.

Durations According to Dates

For the indexed surgery, the date of randomization or admission to the intensive care unit corresponding to the surgery date will serve as day 1.

Take, for example, the calculation of the postoperative hospital stay (in days).

The formula is: (Discharge date from hospital - Date of index surgery) + 1

Exact dates will be tracked and documented.

Analysis of the primary endpoints

The primary endpoint, incidence of postoperative complications as defined by higher than grade I Clavien-Dindo classification at 30 days after surgery will be analyzed using Chi-squared test as crude analysis. Unadjusted risk ratios with 95% confidence intervals will be estimated by two-by-two table with the use of log-Normal approximation or other approximation/numeric methods as appropriate. The effect size will be expressed as risk differences (95% confidence intervals) will be estimated using Wald's likelihood ratio approximation test or other methods appropriate, with the number needed to treat as the reciprocal of the risk difference, rounded to the nearest integer.

Secondary Analyses of the primary endpoint

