To better interpret the composite endpoints with different levels of clinical importance. We will repeat analysis of primary outcome using a hierarchical global rank scale by using win ratio method. This method put the greater weight on the more patient centered outcomes with more clinical relevant outcomes (death, life threatening complications) than transient, self-limiting complications. In the present study, the complications with higher grade of Clavien-Dindo classification will be put on higher hierarchy. The global rank endpoint will be constructed by comparing each patient in the intervention group to each patient in the control group (a total of $m \times n$ comparisons where m is the total number of patients in the intervention group and n the number of patients in the standard care group) for the prespecified order of the endpoints. Based on which patient performs better in each pair, the group they belong to would be declared the 'winner'. This would give us the total number of winners in each group and our test statistic would be based on this. In the case of the win-ratio method, for instance, the statistic would be the number of winners in the intervention group divided by the number of winners in the control group. A 95% confidence interval for the win ratio will be calculated with the bootstrap

method. To make the pairwise comparison, the priority order of endpoints are:

1. Clavien-Dindo grade V
2. Clavien-Dindo grade IVb
3. Clavien-Dindo grade IVa
4. Clavien-Dindo grade IIIb
5. Clavien-Dindo grade IIIa
6. Clavien-Dindo grade II
7. Clavien-Dindo grade I
8. No complications happened

Finally, We will repeat primary analysis on primary endpoints by using mITT, as-treated and PP data-sets.

For scenarios where events are rare in the defined order above, the following orders and composites shall be considered:

1. Clavien-Dindo grade V
2. Clavien-Dindo grade IV
3. Clavien-Dindo grade III
4. Clavien-Dindo grade II
5. Clavien-Dindo grade I
6. No complications happened

OR

1. Clavien-Dindo grade V
2. Clavien-Dindo grade III - IV

3. Clavein-Dindo grade I - II
4. No complications happened

Estimating the effect of the intervention for participants who undergo surgery under general anesthesia

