The COIN trial is to evaluate whether colloid bolus infusion before anesthesia induction improves clinical outcomes compared to crystalloid bolus infusion in patients undergoing non-cardiac surgery under general anaesthesia. In clinical practice, in rare circumstance, surgery may be delayed or canceled, and the participant may not undergo surgery before the outcome is collected. Similarly, in rare instances, the surgery may be conducted under local anesthesia. These participants will be excluded and the left participants who undergo surgery will be analyzed as mITT datasets.

Protocol Deviations

The number and percent of patients with at least one protocol deviation will be summarized for each treatment arm. These include received wrong fluid, received wrong dose of fluid, or with infusion duration exceeds 15 min. These participants will be excluded and the left participants will be analysed as PP datasets.

Analysis of the secondary endpoints

Incidence of hemodynamic instability within 20min of anesthesia induction.

Incidence of post-induction hypotension will be analysed using a logistic regression model, adjusting for ASA grade, gender, age, NPO duration, fluid administration within 12 hours prior to surgery (y/n), history of hypertension.

Intraoperative consumption of vasopressors

Intraoperative consumption of vasopressors will be analyzed using a linear regression model, adjusting for ASA grade, gender, age, NPO duration, fluid administration within 12 hours prior to surgery (y/n), history of hypertension.

Length of postoperative hospital stay

Length of postoperative hospital stay will be analysed using a competing-risk time-to-event model, considering mortality as a competing risk for hospital discharge. The model will include adjustment for planned surgical procedure complexity grade, ASA grade, gender, age, baseline hemoglobin, and baseline creatinine. In case of convergence issues, singular matrix, or other numeric complexity, appropriate data transformation, or dimension reduction methods will be used.

For each treatment arm, we will present median and IQR for length of hospital stay for patients survived to hospital discharge. The number and percentage of patients survived to discharge and number and percentage of patients who died will also be reported.

Rate of ideal postoperative recovery within 5 days of surgery

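### The per-protocol and as-treated sets get only the crude primary analysis, although membership or grouping in them depends on events after randomisation; an adjusted estimate should be added

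*SAP*

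**What the plan says.** Under Analysis of the primary endpoints, the primary endpoint "will be analyzed using Chi-squared test as crude analysis", with unadjusted risk ratios and risk differences. Under Secondary Analyses of the primary endpoint, "the adjusted analysis of primary endpoint will use a logistic regression model"; its covariates are surgical complexity, ASA grade, gender, age, baseline haemoglobin and creatinine, fasting duration and fluid in the 12 hours before surgery. The same section then states: "We will repeat primary analysis on primary endpoints by using mITT, as-treated and PP data-sets". It does not carry the adjusted model over to those sets.

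The sets are defined under Datasets for Analyses and Protocol Deviations:

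- As-treated: "The as-treated population is defined by the treatment that was actually received during the trial". Crossovers are named as one reason for regrouping.
- Per-protocol: "The Per-Protocol (PP) population consists of all patients who received the assigned treatment without significant deviations from the protocol". Further, "Participants with treatment interruptions will be excluded from the PP analysis".
- Deviations leading to per-protocol exclusion: "These include received wrong fluid, received wrong dose of fluid, or with infusion duration exceeds 15 min". The count and percentage of patients with at least one deviation are to be summarised by arm.

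The SAP also limits the weight of these analyses. Datasets for Analyses calls them supplementary and makes intention-to-treat the governing principle. Corrections for Multiple Testing calls everything beyond the single primary analysis exploratory.

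**The concern.** The SAP introduces covariate adjustment in order to deal with confounding. It applies that adjustment to the randomised comparison, where confounding is least expected, and leaves the two non-randomised comparisons crude. The per-protocol set is reached by dropping patients after randomisation, the as-treated set by regrouping them.

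The SAP itself suggests that some departures may be related to prognosis. Datasets for Analyses foresees that an investigator may discontinue a patient's participation in that patient's interest, especially when a serious adverse event is suspected to be related to the intervention. Such patients stay in the intention-to-treat analysis. Where this meant an interrupted infusion, they would leave the per-protocol set. Because the volume is set per kilogram and must run within 15 minutes, the required rate rises with weight, so slow infusions need not be a random subset either.

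At stake is how the supplementary results are read. General analysis Principles attaches an estimate, a 95% confidence interval and a two-sided P value to analyses of the primary outcome, and nothing warns that these two comparisons are not randomised. A gap between such a result and the intention-to-treat result could be taken as a treatment effect when it reflects who was dropped or moved.

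**Working it through.** **Inputs from the SAP (Sample Sizes).** Event risks 33% and 26%, a difference of 33 − 26 = 7 points; 2020 patients, 1010 per arm; 10% drop-out, so 1010 × 0.9 = 909 evaluable per arm.

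**The plan's own figure.** A two-sided 5% test with 90% power for 33% versus 26% needs 890 per arm. Then 890/0.9 = 989 per arm, or 1978 in total, within 3% of 2020. The 7-point difference is therefore the right yardstick. The sample size itself does not bear on this point.

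**Assumptions.** The SAP gives no rates of deviation or crossover and no event risk among affected patients. All values below are assumed, with no true effect and a 33% risk in both arms.

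**Per-protocol set, both arms losing patients.** If a share *f* of an arm is excluded and those patients have risk *r*, the retained risk is (0.33 − *f·r*)/(1 − *f*). With *r* = 0.45:

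- 3% excluded: (0.33 − 0.03 × 0.45)/0.97 = 0.3263
- 8% excluded: (0.33 − 0.08 × 0.45)/0.92 = 0.3196
- 12% excluded: (0.33 − 0.12 × 0.45)/0.88 = 0.3136

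8% against 3% gives a spurious difference of −0.67 points; 12% against 3% gives −1.27 points, both in favour of the arm with more exclusions. Relative to the design effect this is 0.67/7 = 10% and 1.27/7 = 18%.

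The standard error of the risk difference after these exclusions is about 2.3 points, so the bias is about 0.3 to 0.55 standard errors. A nominal 5% test would reject in about 6% to 9% of such trials.

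**Per-protocol set, exclusions from the colloid arm only.** Same formula, with the other arm at 33% and 909 evaluable per arm before exclusion:

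| Excluded | Bias at r = 40% | at 50% | at 66% | Rejection rate, r = 40% to 66% |
|---|---|---|---|---|
| 1% | −0.07 | −0.17 | −0.33 | 5.0% to 5.3% |
| 2% | −0.14 | −0.35 | −0.67 | 5.1% to 6.1% |
| 5% | −0.37 | −0.89 | −1.74 | 5.3% to 12.2% |
| 10% | −0.78 | −1.89 | −3.67 | 6.4% to 37.5% |

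Bias is in percentage points. With equal exclusion and equal risk among the excluded in both arms, it is zero.

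**As-treated set.** Here patients are moved, not dropped. If a share *f* of the colloid arm with risk *r* received crystalloid, the groups become (0.33 − *f·r*)/(1 − *f*) and (0.33 + *f·r*)/(1 + *f*). For *f* = 2% and *r* = 50%: 0.3265 − 0.3333 = −0.68 points.

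| Crossing over | Bias at r = 50% | at 66% |
|---|---|---|
| 1% | −0.34 | −0.66 |
| 2% | −0.68 | −1.32 |
| 5% | −1.70 | −3.31 |

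For the same share of patients this set is more sensitive, because each move changes both groups.

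**The case against.** **No primary inference is touched.** This stands. A reader might infer that the trial's conclusion or its type I error is at risk. The documents do not support that: intention-to-treat governs, and these analyses are supplementary and exploratory. Nor does the SAP say that they serve to check for dilution of the primary result.

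**Bias is not inevitable.** This also stands. A reader might infer that a crude per-protocol result must show selection as treatment effect. That needs departures that both differ by arm and relate to prognosis. Weight, venous access and preoperative condition are balanced by randomisation, caregivers are blinded, and both arms receive the same volume per kilogram by pump. Only a reaction to the fluid is clearly arm-specific, and no rate is given for it. For a single short infusion, deviations may be few.

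**Safeguards exist.** "The exclusion list will be verified by the steering committee prior to lock of the database", and deviations are counted by arm. This is partly an answer. Verification before lock limits data-driven exclusion but does not restore comparability. The planned count does not ask for reasons, and interruptions are not among the listed deviations.

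**The crude repeat has a use.** A reader might infer that it should be replaced. That does not follow: the same method on a different set isolates the effect of changing the set, while changing set and model together loses this. It is a reason to add the adjusted analysis and keep the crude one.

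**Adjustment may not reach the cause.** This stands in part. The listed covariates omit weight and BMI, and selection through a reaction to the fluid need not be captured by any baseline variable. Adjustment can reduce the bias, but how much cannot be stated from the documents.

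**Conclusion.** The point holds as a limited weakness in the supplementary analyses. The SAP plans only an unadjusted comparison for two sets that randomisation no longer protects, while a suitable covariate model for the same endpoint stands in the same section.

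The size depends wholly on assumed rates. It is about 0.7 to 1.3 points at 8% to 12% versus 3% exclusion with a 45% risk among the excluded, and below 1 point when 1% to 2% of one arm is excluded. It becomes material only at roughly 5% to 10% one-sided departure with a clearly raised risk. Selection by exclusion describes the per-protocol set only; in the as-treated set the mechanism is regrouping. The change is worth making because it is cheap and guards against misreading.

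**What to change.** In Secondary Analyses of the primary endpoint, keep the crude repeat on all three sets. For the per-protocol and as-treated sets, add the covariate-adjusted model from the same section, with BMI added (already needed for the prespecified subgroups), reported as an adjusted risk difference and risk ratio.

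In Protocol Deviations, extend the summary to exclusions, interruptions and crossovers, by arm and by reason.

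State that both sets are non-randomised comparisons, in which adjustment reduces confounding but may not remove it.

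Cost: a few sentences of SAP text, a little more analysis work and one more supplementary estimate per set. The model exists and BMI is the only new covariate; the sample size and the primary analysis do not change.
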